Measuring Target Engagement: Auditory Processing Speed (APS) Learning is the target to be engaged in this application. APS is tested via the TCT “Sound Sweeps” training exercise (Posit Science; brainhq.com): a frequency discrimination time-order judgment task^{66,67}. Subjects hear pairs of frequency-modulated sound sweeps and indicate whether they perceive each sweep as becoming higher or lower in pitch (Fig. 3). Sweep duration, frequency range and interstimulus interval get shorter after correct responses, but longer after incorrect responses. APS is calculated based on the shortest duration of stimuli that subjects discriminate correctly. Before and after each training session, subjects complete an APS assessment to quantify simple auditory learning (**APS pre- minus post-training**)²⁹. This “auditory learning” is believed to be a critical component of TCT-based clinical and neurocognitive gains and **serves as our operational measure of target engagement**^{26,30,68}.

Memantine acutely enhances APS learning: Our preliminary findings provide evidence of target engagement for this PACT model: compared to PBO, one dose of MEM (20 mg) was associated with greater APS “learning” across 1-h of a “Sound Sweeps” training session of TCT. Consistent with our previous report of amphetamine (10 mg), MEM did not alter APS, but it significantly enhanced auditory learning over 1-h of training in both HS and SZ patients, and these gains in learning were not state-dependent and lasted at least 1 week⁴³.

[figure not shown]

Fig. 3. MEM effects on Sound Sweeps learning. A. Subjects identify “sweep direction” of frequency modulated tones; adaptive trials increase in difficulty as subject learns. B. Auditory Processing Speed (APS, in ms; smaller # = better discrimination) is calculated both pre- and post-training. APS “learning” is defined as “APS pre minus APS post”. C. In a within-subject design, 20 mg MEM significantly enhanced APS learning in SZ patients (diagnosis by drug: F=5.0, p<0.035). D. MEM-induced gains in APS learning “carried forward” to pre-testing 1 wk later; this did not happen if either no pill or PBO was received the previous week (Order: F<1.0; drug: F=4.95, p<0.04); order by drug (F<1.0). Thus, MEM-enhanced learning is not “state-dependent”.

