Staff assessing outcome measures are blind to treatment arm, and for some measures receive training using videotaped and practice interviews until achieving high (ICC>.80) reliability based on 20 assessments by 2 raters. We achieve high inter-rater reliability (e.g., ICC>0.85 for PANSS total), and check for rater drift each 90d.

Specific Procedures: TCT is completed with a dedicated room and equipment. Staff trained with a UCSD-developed “TCT Clinician Competence Assessment” monitor TCT, clarify instructions and provide encouragement as needed. **In the initial “biomarker testing” session (Test 1),** subjects complete 1-h of Sound Sweeps to generate a “Pre-Training APS score” as described previously (Fig. 3) under identical circumstances and timelines as for the Test 2 session described below. Treatment group assignment (PBO vs. MEM) is then made using stratified random sampling (above) and 5-7 days later patients ingest either PBO (n=27) or 20 mg MEM (n=27) 240 min before completing the Sound Sweeps session (“Test 2”). MEM effects on APS learning are assessed both within-subject (APS (Test 1 - Test 2) for MEM group subjects: a key measure of **MEM sensitivity**) and between subjects (APS Test 2, PBO vs. MEM groups). After Test 2, all subjects are prescribed daily PBO or MEM using a standard titration schedule (MEM 5 mg at hs→ 5 mg bid→ 5 mg am/10 mg hs→ 10 mg bid over 3 weeks). Participants return to the laboratory to complete 1h TCT per our established procedures^{2,34}, which includes 5 modules of auditory/verbal processing exercises. Each module increases in difficulty as performance improves: **1) Sound Sweeps; 2) Syllable Identification:** Patients distinguish between 2 similar phonemes (e.g., “ba” vs. “da”), differing only in their voice onset time; **3) Word Matching:** Subjects match short similar-sounding consonant-vowel-consonant words (e.g., bad, dad); **4) Listen & Do:** Subjects reconstruct a spoken series of instructions and use a computer mouse to click icons on the screen in a specified order. This exercise is designed to stimulate verbal WM processes supported by the lateral PFC as well as premotor and motor processes. **5)**

Table 1. “Go” criteria: #1, plus at least one of #'s 2, 3 & 4 ($d>0.5$)

1. **Target engagement:** APS learning, MEM > PBO, p<0.05
2. **Greater** clinical, neurocognitive **or** functional gains:
 - ↓PANSSt, ↑MCCB-C **or** ↑Fnxn: MEM+TCT > PBO+TCT
3. **Faster** clinical, neurocognitive **or** functional gains:

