Aim 1 – Confirm target engagement: The primary dependent measure of target engagement is MEM-enhanced APS learning. APS learning is defined as the reduction in Sound Sweeps APS threshold (ms) Test 1 to Test 2 assessment. Target engagement was demonstrated in Fig. 3⁷⁶, and will be confirmed if APS learning is increased by MEM (note that MEM and PBO groups are matched by Test 1 PBO performance via stratified randomized assignment). As appropriate, effect sizes and inferential statistics are based on standard regression or LME models with random intercepts. A significant interaction between contrast coded drug (PBO vs. MEM) and Test (Test 1 vs. Test 2) predictors on APS learning is a “Go” criteria and confirms target engagement.

Aim 2 – Test clinical, neurocognitive and functional impact of MEM on TCT, and its relationship to target engagement: We will determine if MEM+TCT produces greater, faster or more durable clinical, neurocognitive or functional gains from baseline, compared to PBO+TCT, over a 30-session course of TCT. A Cohen’s $d > 0.5$ for the main effect of drug (PBO vs. MEM) or drug x session (#10, 20, 30) interaction in an LME model is the primary “Go” criteria. The effect of drug assesses “greater” gains. Reverse Helmert contrasts for session assesses “faster” gains. A separate model comparing differences in outcomes at 12-weeks post-TCT assesses “more durable” gains. Secondary analyses will examine whether change in MEM-enhanced APS learning (“within-subject” target engagement; Aim 1) predicts gains in Aim 2 outcome measures.

Aim 3 – Biomarkers of MEM-induced gains: We will determine if baseline levels of specific neurocognitive or EEG-based measures, or changes in specific measures with initial MEM exposure (Test 2 vs. 1), predict greater sensitivity to MEM-enhanced neurocognitive, clinical or functional gains over 30-h of TCT. Regression analyses will assess whether specific candidate biomarkers predict MEM-enhanced gains in outcome measures.

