1. We don’t know how MEM works. MEM is described as an uncompetitive low-affinity NMDA receptor antagonist with rapid blocking and unblocking ability. It is widely used to treat Alzheimer’s Disease^{44,45}, but the cellular mechanisms responsible for MEM’s clinical effects are a source of controversy, and the present application is fully agnostic to such mechanisms. One relevant clinical effect of MEM is to enhance verbal communication in Alzheimer’s patients^{108,109}, which might reflect gains in auditory discrimination. It also has positive activity in cognitive measures in both healthy animals and a range of human and animal models for dementia, depression, ischemia and neuroinflammation^{110,111}. Thus, consistent with an RDoC framework, the impact of MEM on disease states is defined more by a dimension of cognition, than by a diagnostic entity. MEM enhances hippocampal long-term potentiation (LTP), and reverses an experimentally-induced loss of LTP¹¹¹; it also alters excitation/inhibition (E/I) dynamics in frontal circuitry implicated in models of SZ neuropathology¹¹² and associated with MMN and cognitive deficits in SZ¹¹³. We have also recently shown that acute 20mg of MEM normalizes novel measures of E/I balance in SZ patients⁶³. **What we do know about MEM**, however, is that it acutely increases EAIP (Fig. 2) and Sound Sweeps APS learning in SZ patients (Fig. 3); here, we ask whether

such gains accompany daily MEM use and translate into an augmentation of TCT's clinical benefits.

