11. “Negative results... [will] guide further intervention development”? This R33 has clear ‘Go/No-Go’ criteria. If target engagement is not confirmed, we will conclude that this design setting is unsuitable for detecting robust MEM group effects on APS learning. Based on the data (e.g. evidence of MEM bioactivity), we will develop testable hypotheses (e.g. cohort differences) that might account for differential outcomes in the present application. Even if there are not robust MEM effects on APS learning (target engagement), it is possible that heterogeneity in MEM APS sensitivity might reflect meaningful subgroups of patients (e.g. low vs. high attention/vigilance), and that APS MEM sensitivity might still predict (correlate with) MEM enhancement of TCT therapeutic effects. In other words, a lack of a group difference (placebo vs. MEM) would not preclude the utility of MEM APS sensitivity as a predictive biomarker. Conversely, even if target engagement is confirmed, it is possible that group differences (placebo vs. MEM) in therapeutic gains might not be detected. A “valid” negative outcome (e.g. lack of positive MEM effects on outcome measures despite evidence of target engagement and adequate TCT exposure) will indicate that MEM-enhanced APS learning is not sufficient to enhance TCT effects in a clinically-defined SZ cohort. Analyses will then determine if MEM enhances TCT effects in biomarker-defined SZ subgroups. A failure to detect such subgroups would suggest a dissociation between target engagement in the first Sound Sweeps session and therapeutic benefit after 30-h of TCT.

12. This work is feasible. Our study team includes 2 Board Certified Psychiatrists (NS, YJ) with SZ clinical trial experience, a licensed Clinical Psychologist/Neurophysiologist and PI of a BBRF-funded trial of biomarker predictors of TCT in SZ patients (GL), an expert statistician with a career focus on analytic pathways from biomarkers to clinical function in SZ (MT), a UCSD SZ Research Program with a >30 y history of recruiting and testing thousands of psychosis patients in studies with ERPs and other biomarkers proposed in this R33 (published retest stability with 1-year follow-up¹⁴⁰), as well as double-blind, PBO-controlled trials of putative pro-cognitive agents (including MEM) in SZ patients and HS^{48,49,74,104}. We completed and published extensively on a 30-session clinical trial of TCT in SZ patients and with many of the same biomarkers proposed herein.

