13. Why an R33 and not a full Confirmatory Efficacy Trial? While this work provides a strong empirical justification for MEM target engagement, this evidence is insufficient to justify moving to a full, large scale, Confirmatory Efficacy trial with PACT at this time. We acknowledge that MEM may enhance TCT-induced APS learning in a single session, but still not enhance, accelerate, or make more durable TCT-induced clinical, neurocognitive or functional gains following a full course of TCT. Even with evidence of target engagement, and its replication and optimization, it is still only a *hypothesis* that enhanced learning during TCT will augment its clinical benefits. In fact, MEM has different neurobiological effects after one (as shown in our preliminary results, Figs. 2-3) vs. multiple doses^{141,142} (as proposed in this application); in some models, it is effective after acute but not chronic dosing¹⁴¹. Consistent with this RFA-MH-18705 (“replicate target engagement and relate change in the... target/mechanism to clinical benefit”), testing this hypothesis, with specific “Go/No Go” criteria, will be the most critical development of the present application. Beyond this critical step, this application will leverage a substantial foundation of findings to explore (i.e. “learn/confirm”) mature hypotheses related to mechanisms and predictors of pro-cognitive therapeutics for SZ.

Section 4 - Protocol Synopsis (Study 1)

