4.3. Outcome Measures

Type	Name	Time Frame	Brief Description
Primary	Auditory Processing Speed (APS) learning	Test 1 and Test 2, one week apart	APS is measured before and after the TCT "Sound Sweeps" frequency modulation session, to determine the amount of "learning", based on the reduction in detection gap (ms). More learning (greater gain in processing speed) with memantine vs. placebo confirms target engagement, which is the primary outcome of Aim 1.
Primary	MCCB Composite	baseline vs. post-TCT session 10, 20 and 30 (approximately 10 weeks), and 12 weeks post-TCT	Change in MCCB Composite performance from baseline is one outcome measure. The MCCB measures 7 cognitive domains: speed of processing, attention/vigilance, working memory (verbal and nonverbal), verbal learning, visual learning, reasoning/ problem solving and social cognition. Details are found in[25, 89, 90]; past studies of drug effects on MCCB performance include[37, 91]. Since the MCCB is assessed multiple times, alternate forms of the HVLT-R and BVMT-R are used in counterbalanced order. MCCB Global Composite T-score (MCCB-C) is the primary neurocognitive outcome measure. Individual MCCB domain T-scores are used in secondary analyses to determine whether an overall effect is driven by specific aspects of neurocognition; TCT effects on verbal learning performance are known to be robust[13], and should be augmented by MEM. Baseline and MEM-enhanced (Test 2 vs. 1) MCCB performance (A/V subscale) will also be tested as potential biomarkers/moderators of MEM PACT efficacy.

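### A null Aim 2 result cannot show that memantine-enhanced learning is insufficient, because no pre-specified analysis compares learning between arms during the 30 training sessions

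*Combined protocol and SAP*

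**What the plan says.** **The inference rule.** Research Strategy, item 11, states that a valid negative outcome, meaning no positive drug effect on outcomes "despite evidence of target engagement and adequate TCT exposure) will indicate that MEM-enhanced APS learning is not sufficient to enhance TCT effects" in a clinically defined cohort. Subgroup analyses follow. If they fail, the text speaks of a dissociation between engagement in the first Sound Sweeps session and benefit after 30 hours.

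**When engagement is tested.** Under Specific Procedures, "5-7 days later patients ingest either PBO (n=27) or 20 mg MEM (n=27) 240 min before completing the Sound Sweeps session" (Test 2). Only then does the treatment phase begin: "After Test 2, all subjects are prescribed daily PBO or MEM using a standard titration schedule". Under Data Analysis, Aim 1, the confirming result is "A significant interaction between contrast coded drug (PBO vs. MEM) and Test (Test 1 vs. Test 2) predictors on APS learning". Section 4.3 gives the time frame of the APS learning outcome as "Test 1 and Test 2, one week apart".

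**What the plan says about repeated dosing.** Item 1 asks whether "such gains accompany daily MEM use and translate into an augmentation of" the clinical benefit of TCT. Item 13 says of memantine that "in some models, it is effective after acute but not chronic dosing".

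**What is measured during or after training.** The paragraph Measuring Target Engagement says: "Before and after each training session, subjects complete an APS assessment to quantify simple auditory learning". Item 6 lists APS plateau as something to explore. EEG and the two speech-in-noise tests (WIN, QuickSIN) are repeated after session 30, and the Biomarkers paragraph says drug augmentation of auditory discrimination gains will be tracked.

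**The concern.** The hypothesis in item 6 is about learning during TCT: the drug enhances it, and enhanced learning produces more benefit. The engagement test comes before the first training session. If memantine enhances learning after one dose but not under repeated dosing, the trial would pass the engagement criterion, show no clinical gain, and record that enhanced learning is not enough. In that case learning would not have been enhanced while patients trained, and the step from target to benefit would be untested.

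A positive Aim 2 result has a related gap. The only specified link from target to outcome uses the acute Test 1 to Test 2 change as a predictor, so a benefit could not be related to learning during training. The group plans to apply this design to other drugs, so a wrong mechanistic reading could affect more than this compound.

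**Working it through.** **Step 1. Where each link is tested.**

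| Link | Analysis in the plan |
|---|---|
| One dose to APS learning | Drug x Test interaction, Tests 1 and 2 (Data Analysis, Aim 1; Section 4.3) |
| Treatment-phase dosing to APS learning in training | None specified in Data Analysis or Section 4.4 |
| Treatment arm to clinical, cognitive and functional gains | Mixed models at sessions 10, 20, 30; separate model at 12 weeks |
| Target to gains | Secondary; uses the acute within-subject change only |

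Formal engagement testing thus covers one session on drug (Test 2) and 0 of the 30 training sessions.

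**Step 2. What a null Aim 2 result after a positive acute test can mean.** (a) Learning was enhanced throughout training and did not help. (b) Learning was not enhanced during training. The specified analyses would look the same under both. Item 11 concludes (a).

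**Step 3. Can (b) be set aside on the documents?** No. Item 13 allows for it. Fig. 3D reports that a gain carried forward one week, but that is retention after a single dose, not continued enhancement under repeated dosing. How far the treatment phase differs from the acute test is also unclear:

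- Design and Specific Procedures describe daily dosing, titrated over 3 weeks while TCT runs at 3 sessions a week, so about 3 x 3 = 9 of 30 sessions fall within titration.
- Sections 4.2.a and 4.4 describe 20 mg taken 60 minutes before each session.
- The Test 2 dose-to-test interval is 240 minutes in Specific Procedures and 1 hour in Section 4.2.a.

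These passages must be reconciled. Either version is repeated dosing.

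**Step 4. The plan's own sample size.** Inputs (Power analyses): d=0.5, 80% power, two-sided alpha 0.05, test-retest correlation r=0.8. For a two-time-point change contrast, the SD is sqrt(2(1-r)) = sqrt(0.4) = 0.632 and

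n = 2 x (1.960 + 0.842)^2 x 0.4 / 0.5^2 = 25.1, so 26 per group.

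The t-based figure is 26.1, so 27. The stated 27 is reproduced, with power at 27 of 0.83 (normal) or 0.81 (t). It covers the acute contrast only.

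**Step 5. What a treatment-phase contrast could deliver.** Illustration, assuming the same SD structure. Power = Phi(d / (0.632 x sqrt(2/n)) - 1.96). The n values are 27 randomised and 18 completers per arm (Subject throughput). Half retention is an assumption; 0.85 is the plan's empirical d.

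| Acute d | Retained | d in training | Power, 27/arm | Power, 18/arm |
|---|---|---|---|---|
| 0.50 | all | 0.50 | 0.83 | 0.66 |
| 0.50 | half | 0.25 | 0.31 | 0.22 |
| 0.85 | all | 0.85 | 0.999 | 0.98 |
| 0.85 | half | 0.425 | 0.70 | 0.52 |

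The 95% half-width is 1.96 x 0.632 x sqrt(2/n): 0.34 with 27 per arm and 0.41 with 18. A non-significant contrast could easily be chance, so it cannot be read as loss of engagement.

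**Step 6. Precision of the null itself.** For a simple between-arm d near zero, the half-width is 1.96 x sqrt(2/n): 0.53 with 27 per arm and 0.65 with 18. Baseline adjustment at r=0.8 multiplies these by sqrt(1 - 0.8^2) = 0.6, giving 0.32 and 0.39. If the true d equals the 0.5 threshold, the observed d falls below it half the time. A null would therefore be limited evidence of insufficiency even under (a).

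**The case against.** The sponsor has a fair reply. Item 11 is hedged: it says a null will indicate insufficiency, confines this to a clinically defined cohort, and itself describes engagement as belonging to the first session. Item 13 openly discloses the acute-versus-repeated issue and gives it as part of the reason for a pilot. Related measures are taken after treatment, and item 6 accepts that early auditory measures or QuickSIN could also show engagement. A null Aim 2 is a No-Go whatever the mechanism.

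This lowers the severity but does not close the gap. Item 6 prefers APS learning as the target closest to the benefit. APS plateau has no time point, model or criterion. None of these measures conditions the item 11 conclusion, and lost engagement is not among the explanations it offers.

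Some stronger readings are tempting and should not be made:

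- *That the plan treats a null as proof.* The wording is weaker than that.
- *That learning in training is never examined.* APS testing around each session is described and a plateau measure is to be explored. What is missing is a pre-specified comparison between arms.
- *That all 54 participants will supply the data.* The plan conservatively expects 18 completers per arm.
- *That 10 mg maintenance doses cannot engage the target because 10 mg equalled placebo acutely.* That result comes from single-dose tests and does not bear directly on repeated doses totalling 20 mg a day.

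**Conclusion.** The concern stands at moderate severity. Acute engagement plus a null Aim 2 result does not support the conclusion that memantine-enhanced learning is insufficient, because no specified analysis establishes that learning was enhanced while patients trained. No Go criterion, primary analysis, error rate or sample size is affected; what is at risk is the mechanistic conclusion carried into later work.

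A reader might go further and infer that engagement is lost under repeated dosing. The documents do not show this. They show only that it is possible and would go undetected by the specified analyses.

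The conclusion rests on the absence of a treatment-phase APS model in Data Analysis and Section 4.4. The power figures rest on carrying d and r over from the acute test, which the documents do not establish. Feasibility of the remedy rests on the per-session APS scores being stored: Section 4.3 lists APS only at Tests 1 and 2.

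**What to change.** 1. **Pre-specify a treatment-phase engagement analysis before unblinding.** Use a secondary mixed model of Sound Sweeps APS by arm around sessions 10, 20 and 30, in all randomised participants with data. Take as baseline the pre-training APS at the first TCT session, after Test 2. A Test 1 baseline would let the gain carried over from the single Test 2 dose (Fig. 3D) pass as sustained engagement. Use within-session learning as support. Report the estimate with a 95% confidence interval. First confirm that the per-session APS scores are stored.
2. **Reword item 11.** Conclude that enhanced learning is not sufficient only when engagement is shown both acutely and during training, with the criterion stated in advance (for example, an interval that excludes zero in favour of memantine). Otherwise state that engagement during training was not demonstrated and that the target-to-benefit hypothesis remains untested, without claiming that engagement was lost.
3. **Use the treatment-phase measure beside the acute one** in the secondary analysis of engagement against gains.
4. **Reconcile the regimen and timing passages**: Design and Specific Procedures against Sections 4.2.a and 4.4.

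**Cost.** SAP wording and one added model, with no new visits if the scores are stored; if they are not, APS assessments at these sessions would have to be added. Precision is limited at about 18 completers per arm. Adaptive training plateaus, so late within-session learning shrinks. The proposed baseline falls after randomisation and the arms may already differ there, so the contrast is explanatory and should be labelled so.
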